4.2.1 Primary Endpoint

The primary endpoint is to determine the impact of losartan on LT fibrosis in HIV infected, ART treated adults. This will be determined by measuring the amount of collagen deposition in LT and the integrity of the FRCN using immunohistochemistry (IHC) and quantitative image analysis (QIA).

4.2.2 Secondary Endpoints

There are 4 secondary endpoints:

1. We will assess the impact of losartan on immune reconstitution and T-cell function by measuring:

- ⇒ Frequency of CD4+ T cells, TUNEL+CD3+CD8+ T cells and cells expressing TGF-beta and lymphotxin-beta in LT using IHC.
- ⇒ Serum levels of IL-7 and TGF-beta using ELISA.
- ⇒ The immune response to HPV vaccination using flow cytometry to identify cells stimulated by specific HPV peptides.

2. We will determine the impact of losartan on immune activation in HIV infected, treated individuals by determining:

- ⇒ Frequency of activated T-cell populations (specifically CD3+CD4+CD38+, CD3+,CD8+CD38+, CD4+Ki67+ and CD8+Ki67+ T cells) in LT using immunofluorescence staining.
- ⇒ Percentage of activated T cells, macrophages and dendritic cells in PBMCs and LT using flow cytometry.
- ⇒ Intracellular levels of the inflammatory cytokines IL-17, IFNg, IL-2, TNF, IL-10, and GM-CSF in PBMCs and LT using cytokine staining.
- ⇒ Plasma levels of additional inflammatory markers including LPS, sCD14, I-FABP, IL-1b, IL-1RA, IL-6, TNF, amyloid A, CRP, and D-dimer using limulus assay (sCD14) and ELISA (all others).

3. We will assess the potential for losartan to reduce the size of the viral reservoir by determining the frequency of HIV RNA+ and DNA+ cells in LN and GALT using both radiolabeled in situ hybridization (ISH) and RNAscope™ in situ technology.

4. To ensure that losartan is safe and well tolerated when used with ART, we will:

- ⇒ Perform an intensive pharmacokinetics experiment in all HIV infected subjects at month 1 of the study (when losartan is at steady state).
- ⇒ Measure levels of ARTs and losartan in plasma and PBMCs quarterly over the 30-month study period.
- ⇒ Measure intracellular levels of losartan and ARTs in LT at month 30.

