3.2 Secondary Objectives

To determine the impact of losartan on immune reconstitution and T- cell function, immune activation, HIV viral reservoir size, and to determine any potential drug-drug interactions between losartan and ART.

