Samples obtained for pharmacokinetic analysis will be immediately sent to [name] laboratory and will be analyzed in semi real-time. Levels of losartan and all ARVs that an individual subject is taking will be monitored to ensure that subjects are not exposed to supratherapeutic levels of any drug, that losartan does not decrease levels of any ARVs, and that the active metabolite of losartan is within the expected range. Results of these analyses will be communicated to the PI as soon as they are available. If losartan is found to either increase or decrease levels of a particular ARV, the IRB will be notified and all enrolled subjects taking that ARV will be contacted and the finding explained. Depending on the type of drug-drug interaction, toxicity labs and/or HIV VL will be obtained within 3 days of obtaining the drug level results. If dose adjustments can be used to overcome these interactions, they will be made if the subject is willing. If dose adjustments are not possible, subjects taking the ARV will be withdrawn from the study and the protocol will be amended so that no additional subjects taking that ARV will be enrolled. If losartan metabolite levels are found to be lower than the expected range, the losartan dose will be increased. If losartan metabolite levels are higher than expected, toxicity labs will be obtained and the dose will be decreased. After any dose adjustments of losartan or ARVs, follow up drug levels will be monitored closely to ensure that target levels have been achieved.

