11. STATISTICAL CONSIDERATIONS

11.1 Overview and General Design Issues

From the perspective of statistical analysis, the aims of the proposed study are all quite similar: to determine if a randomized intervention has an impact on a longitudinally observed outcome. Despite this similarity, there are differences in the frequency with which some outcomes of interest will be observed and this will impact the details of how the analysis will be conducted. In particular, some variables will be measured quarterly (those that are assessed in peripheral blood, such as LPS, IL-6, TNF and ICAM-1) while those variables assessed via biopsy (such as the number of Ki67+ cells and the magnitude of the FDC pool) will only be available at baseline, and 12 and 30 months after initiating treatment with losartan. The approach that will be used to test for treatment effects in both scenarios will involve fitting mixed models with treatment group indicators, time effects and interactions between time and treatment group to allow for testing for differences in rates of change between the 2 groups. What will differ between the 2 scenarios will be the modeling strategy, as the data that is more frequently observed will permit more sophisticated modeling strategies. These strategies include allowing for nonlinear trajectories via cubic splines and more flexible covariance structures. These models will be fit via restricted maximum likelihood and tests for differences between the treatment groups will be conducted using Wald tests. Standard diagnostics will be employed to assess the adequacy of the fit and remedial measures (e.g. transforming the outcome variable) will be employed as appropriate. The most current version of the statistical software R and the lme package will be used to fit models and examine the data. With 25 subjects per group the study should have adequate power to find strong effects; however losartan has not previously been used in the proposed context.

Analysis of data from the MRI substudy will be descriptive in nature. We are seeking to identify MRI methods that will render an image of the inguinal lymph node that is about to be excised. We will compare

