collagen signal by MRI with collagen content measured by trichome stain. Analysis of PK data will include a comparison to previous data collected from HIV infected persons using a similar protocol. We will determine if blood and tissue levels of drug are similar or if they are statistically greater, or smaller than those historical controls.

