11.3 Enrollment/Stratification/Randomization/Blinding Procedures

HIV infected subjects will be randomized to receive losartan or placebo in a 1:1 manner using ordinary methods for generating random deviates. Study staff (other than those in the IDS pharmacy) and participants will be blinded to the random assignments of all HIV infected study participants. All study drug will be supplied in identical containers.

The two-photon microscopy sub-study of the HIV infected subjects requires 5 participants on losartan and 5 on placebo. Investigators are blinded to treatment assignment. To be able to ensure we have the 5 on losartan and 5 on placebo we will give the list of all subjects who agree to the sub-study to the investigation pharmacist who maintains the blind. They will identify the ten participants we should use for the sub-study.

Blinding will be maintained until all data are entered into the study database, all study endpoint data and other data included in the final analysis have been verified and the data are ready for final analysis. This will be explained to participants as part of the study. Unblinding will occur according to standard operating procedures as per section 9.13.

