11.5 Final Analysis Plan

As detailed in section 11.1, once all of the data is available, mixed effects models will be used to test for differences between treatment groups using standard methods for the analysis of longitudinal data. Conventional significance levels will be used and the fit of the models will be assessed using standard tools (e.g. residual plots).

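### The ART drug-interaction endpoint seeks reassurance, but the analysis offers only difference tests with no no-effect limit or confidence interval, so a non-significant result cannot show that an interaction is absent

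*Combined protocol and SAP*

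**What the plan says.** - **Aim.** Section 3.2 sets the objective "to determine any potential drug-drug interactions between losartan and ART". Section 4.2.2 (item 4) words it more strongly: "To ensure that losartan is safe and well tolerated when used with ART, we will". Three tasks follow: intensive PK at month 1, quarterly plasma and PBMC levels, and tissue levels at month 30.
- **Trigger for action.** Section 7.2 monitors levels in semi real-time, in part to confirm "that losartan does not decrease levels of any ARVs". Action follows "If losartan is found to either increase or decrease levels of a particular ARV". No size of change, reference range or test defines that finding for an ARV.
- **Analysis.** Section 11.1 treats the study aims as statistically alike, plans mixed models, and says that "tests for differences between the treatment groups will be conducted using Wald tests". Section 11.5 adds "Conventional significance levels will be used". The one analysis sentence specific to PK, "We will determine if blood and tissue levels of drug are similar or if they are statistically greater, or smaller than those historical controls", appears to concern the uninfected volunteers and gives no limit or interval either.
- **Design.** "HIV infected subjects will be randomized to receive losartan or placebo in a 1:1 manner" (Section 11.3), with no stratification by ARV. Section 5.2 requires stable ART but no particular drug. The schedule in Section 8.2 marks no PK assessment at Day 0. Section 11.2 gives power for collagen only.

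**The concern.** A test for a difference can support the statement that losartan changes an ARV level. When it is not significant, it cannot support the statement that losartan leaves the level unchanged. That needs a stated limit for a negligible change and an interval lying inside it, and the plan has neither.

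The question is also asked drug by drug, because Section 7.2 acts on a particular ARV. Each comparison uses only the subjects who share that drug. Without a pre-losartan profile, it carries the full between-subject variability.

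Section 2.2 says that losartan-ARV interactions have not been studied extensively, so this trial's statement on combined use may be relied on. Undetected lowering of ARV exposure could put viral suppression at risk.

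**Working it through.** **1. The plan's own power figure.** Section 11.2 gives SD 0.81 (log scale), 25 per group and differences of 0.5/0.6/0.7/0.8. The normal approximation, two-sided 0.05, is Φ(d / (0.81·√(2/25)) − 1.96). For d = 0.5 this is Φ(0.5/0.229 − 1.96) = 0.588. The four results are 0.588/0.745/0.863/0.937, matching the stated 0.59/0.75/0.86/0.94. An exact t calculation gives 0.571/0.728/0.849/0.928. The plan's table is therefore sound, and conventional significance can be taken as two-sided 0.05. It says nothing about PK.

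**2. Largest possible number at month 1.** Section 4.1 plans 63 enrolled (50/(1 − 0.20) = 62.5), and Section 9.7.2 replaces withdrawals before Month 1. So up to 63/2, about 31 per arm, could contribute if every subject took the same ARV; the completer number is 25.

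**3. Power to find a 25% fall in exposure.** Assumed: CV 30, 50 or 60%; 8, 12, 25 or 31 per arm on the ARV; one time point.

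- Log-scale SD: σ = √ln(1 + CV²) = 0.294, 0.472, 0.555.
- Noncentrality: ln(1/0.75) / (σ√(2/n)), with the two-sided 0.05 t critical value on 2n − 2 df.
- Example, CV 50% and n = 8: SE = 0.472·√(2/8) = 0.236; noncentrality = 0.288/0.236 = 1.22; critical value 2.145; power 0.21.

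| Per arm on the ARV | CV 30% | CV 50% | CV 60% |
|---|---|---|---|
| 8 | 0.45 | 0.21 | 0.16 |
| 12 | 0.63 | 0.30 | 0.23 |
| 25 | 0.92 | 0.56 | 0.44 |
| 31 | 0.97 | 0.66 | 0.52 |

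For a halving of exposure at 8 per arm, power is 0.99/0.78/0.64.

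**4. What a null result leaves open.** At 8 per arm and CV 50%, the 90% CI multiplies and divides the estimated ratio by exp(1.761 × 0.236) = 1.52. An estimate of exactly 1.00 would have a CI of 0.66 to 1.52, so a fall of about a third is not excluded.

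**5. What an interval rule would deliver.** With a true ratio of 1, CV 30% and purely illustrative limits of 0.80 to 1.25, the 90% CI falls inside the limits with probability about 0.04 at 8 per arm, 0.16 at 12 and 0.68 at 25.

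**The case against.** **The endpoint is about detection.** Section 3.2 speaks of determining interactions, and the wording in 4.2.2 can be read as a purpose clause before three measurement tasks. A reader might infer that a non-significant test will be reported as no interaction. No section says so, and the only text that contrasts similarity with a statistical difference appears to concern the uninfected volunteers. This part stands. The defect is that the plan has no rule able to support the reassurance it names, whatever is later written.

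**Section 7.2 is not a significance test.** It follows each subject's own drug levels, and nothing ties its trigger to the Wald tests. Section 11.1 also does not say how its longitudinal models apply to a single month-1 profile. Both points are correct. They leave the Section 7.2 criterion undefined, and Section 11 remains the only stated inference between arms.

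**Safety does not rest on a null PK test.** Viral load and safety labs are repeated (Sections 8.1.5 and 8.2). Toxicity labs and/or viral load follow within 3 days of the drug-level results when an interaction is found (Section 7.2). Adverse events are collected and a DSMB reviews the trial (Section 10.1.1). These safeguards are real and lessen the risk to participants. They do not show whether losartan alters a given ARV's exposure.

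**Power may be adequate.** With 25 or more per arm on one drug and CV up to 50%, a 25% fall is more likely found than missed, and quarterly levels may add information. This also stands.

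**Conclusion.** The concern holds in a limited form. Endpoint 4 names a no-harm aim, yet the plan states no no-effect limit, interval, PK variability or number per ARV. A non-significant difference therefore cannot show absence of an interaction. This does not depend on any assumed figure.

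The size does depend on assumptions: CV 30 to 60%, 8 to 31 subjects per arm sharing the ARV, and one time point. On these, a 25% fall is more likely missed than found at 8 per arm at every CV shown, and at 12 per arm at CV 50 and 60%. At 25 per arm it is usually found at CV 30% and found slightly more often than not at CV 50%.

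Two stronger readings are tempting and unsupported. One is that a relevant interaction would usually be missed: the documents do not say what change is relevant, how variable the ARVs are or how many subjects share each one, and a halving would usually be found even at 8 per arm. The other is that safety with ART rests on this test alone, which the monitoring provisions contradict. The change is worth making, but it concerns a secondary endpoint and not the primary result.

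**What to change.** In Sections 4.2.2 (item 4) and 11.5:

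- For each ARV, report the losartan:placebo geometric mean ratio of month-1 24-hour AUC and of trough, each with a 90% CI, and the number of subjects per arm on that drug.
- Have the study pharmacologist fix limits for a negligible change before unblinding. Conclude that there is no relevant interaction only if the CI lies wholly within them; otherwise report *not determined*.
- In the endpoint wording, replace *ensure* with *estimate*.

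The samples are already planned, so the cost is wording and one agreed set of limits. The downside is that many ARVs will be reported as not determined. On the illustrative limits and CV 30%, a drug with no interaction at all would qualify about 4%, 16% and 68% of the time at 8, 12 and 25 per arm, and less often at higher CVs. The change also leaves the undefined trigger in Section 7.2 to be clarified separately by the investigators.

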4.2.3 Exploratory Endpoints

1. Assess the impact of losartan on frequency of dendritic cell and CD4 T-cell interactions with the FRCn using two-photon microscopy.
2. To develop methods to image collagen content of inguinal lymph nodes using MRI
3. To measure drug levels and pharmacokinetic (PK) profile of antiretrovirals in lymph tissues of HIV uninfected people.

5. STUDY POPULATION

5.1 Selection of Study Population

83% of persons living with HIV/AIDS in the State of Minnesota are male, 50% are white, 32% black (with 10% being African born), 9% Hispanic/Latino, 4% American Indian, and 5% Asian or “Other” (Minnesota Department of Health 2010 data). By focusing on women and minority populations in our recruitment efforts, we anticipate that the demographic profile of our study participants will represent this distribution.

HIV infected subjects will be recruited using our well-established recruitment network in the Twin Cities that involves partnerships with local HIV clinics and community organizations such as the Minnesota AIDS Project. We will also design study specific advertisements and flyers for use in local publications and clinics. HIV uninfected subjects will be recruited through flyers placed around the University of Minnesota and advertisements in local magazines and newspapers.

As above, based on drop-out rates in similar studies we have conducted in the past, we plan to enroll a total of 63 HIV infected subjects to ensure that 50 complete the protocol.

5.2 Inclusion/Exclusion Criteria

HIV infected participants:

a. Inclusion Criteria:

Participants must meet all of the following inclusion criteria to participate in this study:

1. HIV-1 infected.

2. ≥ 18 years of age.
3. Baseline peripheral CD4+ T cell count 200-650 cells/mm³ for at least two measures and no more than one measure outside the range over the 6 months prior to study enrollment.
4. ≥ 12 months of consistent use of antiretrovirals without disruption lasting ≥ 1 week in the period leading up to study enrollment.
5. HIV viral load (VL) < 50 copies/mL for at least two measures over the 6 months prior to study enrollment.
6. No contraindication to proposed study procedures.
7. Women of child-bearing potential must be willing to use a form of effective contraception for the duration of the study. Effective contraception includes hormonal injection, implant or oral medication, IUD, diaphragm, or cervical cap with spermicide. Condoms cannot be used as the sole form of contraception.

b. Exclusion Criteria:

Participants meeting any of the following exclusion criteria at baseline will be excluded from study participation:

1. Use of any immunomodulator within the 12 months prior to study enrollment. An immunomodulator for the purposes of this study is defined as a drug known to either diminish or augment a patient's immune system. Examples of these include, but are not limited to, systemic corticosteroids (use of topical steroids will be permitted), TNF-inhibitors, rituximab, cyclophosphamide, abatacept, cyclosporine, azathioprine, 6-mercaptopurine, methotrexate, sulfasalazine, cyclosporine, tacrolimus, sirolimus, and intravenous immune globulin. NOTE: It is considered permissible for a potential subject to have 1) taken a brief (≤ 2 week) course of oral corticosteroids for acute respiratory illness, 2) received a corticosteroid injection into a joint, and/or 3) inhaled corticosteroids for control of reactive airway disease.
2. Current use of an ARB or ACEi.
3. Current use of rifaximin, fluconazole or lithium given potential for drug interactions with losartan.
4. Prior reaction or intolerance to an ARB or ACEi.
5. Prior diagnosis of a chronic inflammatory disease with serologic or clinical evidence as diagnosed by a primary care physician or specialist. Examples of these include, but are not limited to, systemic lupus erythematosus, rheumatoid arthritis, scleroderma, Sjogren's syndrome, mixed connective tissue disease, psoriasis, polymyositis, dermatomyositis, vasculitis, sarcoidosis, Wegener's granulomatosis, giant cell arteritis, polyarteritis nodosa, gastrointestinal pemphigoid, eosinophilic colitis, Crohn's disease, ulcerative colitis, autoimmune hepatitis.
6. Prior diagnosis of a connective tissue disease with genetic, serologic or clinical evidence as diagnosed by a primary care physician or specialist. (Marfan's syndrome, Ehlers-Danlos syndrome).
7. Screening systolic blood pressure < 110.
8. Estimated Glomerular Filtration Rate (eGFR) of < 30ml/min/1.73 m² within 60 days of study initiation or history of advanced renal disease.
9. AST and/or ALT > 3 times the upper limit of normal within 60 days of study enrollment.
10. Potassium > 5.0 within 60 days of study enrollment.
11. Pregnancy.
12. In women of childbearing age, unwillingness to use birth control for the duration of the study.
13. Breast feeding.
14. Prior vaccination with an HPV vaccine, including Cervarix (GlaxoSmithKline) or Gardasil (Merck).
15. History of hypersensitivity or severe allergic reactions to yeast.
16. At the principle investigator's discretion if not a suitable surgical candidate.
17. Currently undergoing treatment for hepatitis C or treatment completed within the last 3 months
18. History of ≥ 3 previous inguinal lymph node biopsies

HIV-uninfected:

a. Inclusion Criteria

Participants must meet all of the following inclusion criteria to participate in this study:

1. HIV uninfected.
2. ≥ 18 years of age.
3. No contraindication to proposed study procedures.

b. Exclusion Criteria

Participants meeting any of the following exclusion criteria at baseline will be excluded from study participation:

1. Use of any immunomodulator within the 12 months prior to study enrollment (as defined above).
2. Current use of an ARB or ACEi.
3. Prior diagnosis of a chronic inflammatory disease with serologic or clinical evidence (as defined above).
4. Prior diagnosis of a connective tissue disease with genetic, serologic or clinical evidence as diagnosed by a primary care physician or specialist. (Marfan's syndrome, Ehlers-Danlos syndrome).
5. AST and/or ALT > 1.5 times the upper limit of normal at screen
6. At the principal investigator's discretion if not a suitable candidate.
7. Sulfa allergy
8. Pregnancy.

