6.3 Permitted Medications and Procedures

Medications not listed under prohibited medications and the manufacturers' package inserts are permitted during this study. If subjects develop a condition that requires a medical procedure while on study, we will determine impact of this on study participation on a case by case basis. Whenever a concomitant medication or study agent is initiated or a dose is changed, investigators must review the concomitant medications and study agents' most recent package inserts, and Investigator's Brochures to obtain the most current information on drug interactions, contraindications, and precautions.

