6.4 Prohibited Medications

The following drugs are not permitted for HIV subjects while on study:

- Any immunomodulator (defined as a drug known to either diminish or augment a patient's immune system). Examples include, but are not limited to, systemic corticosteroids (use of topical steroids will be permitted), TNF-inhibitors, rituximab, cyclophosphamide, abatacept, cyclosporine, azathioprine, 6-mercaptopurine, methotrexate, sulfasalazine, cyclosporine, tacrolimus, sirolimus, and intravenous immune globulin.
- ACE inhibitors
- ARBs other than the study drug
- Rifampin
- Lithium
- Fluconazole

The following drugs are not permitted for uninfected control subjects while taking Stribild and Prezista:

- Any antiretroviral drugs

- Any nephrotoxic drugs
- Any drugs that are highly dependent on CYP3A for clearance and for which elevated plasma concentrations are associated with serious and/or life-threatening events

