7. STUDY PROCEDURES/INTERVENTIONS

7.1 Description and Potential Risks of Clinical Procedures

7.1.1 Medical History

At screening and baseline visits, an extensive medical history will be obtained (including prior diagnoses, medications, surgeries, etc.). Interval medical histories will be obtained at each subsequent study visit. Only trained designated study staff or physicians will obtain the medical history. History will primarily be obtained by interviewing the subject. If the subject is agreeable and signs a release of information form, medical records may also be obtained and reviewed by the study clinical team. Obtaining a medical history may make subjects feel uncomfortable or embarrassed. There are no other potential risks.

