8.1.2 Baseline Visit

Designated study staff will review medical history with the participant and perform a targeted physical exam (vitals, heart, lung, abdomen, neurologic system). The subject will not be randomized until lab results have been reviewed and found to be within limits designated in the protocol. The designated study staff or principal investigator will sign off on lab results and eligibility criteria on the day of randomization to ensure labs are no more than 60 days old and the subject still meets all eligibility criteria. Blood will then be drawn for CBC, comprehensive metabolic panel (CMP – includes electrolytes, creatinine, and liver function tests), CD4 and VL as well as plasma, serum and PBMCs for study endpoints. Subjects in the two-photon microscopy sub-study will also have an additional 90cc of blood drawn. Inguinal LN biopsy and colonoscopy with ileal and rectal biopsies will be performed (described in detail in section 7.1 above). They will remain in the MCRU for 4 hours after procedures for monitoring.

Following procedures, subjects will be randomized to receive either losartan or placebo. The drug will be dispensed to the participant to begin administration on that day. At this baseline visit, participants will start losartan or matching placebo at 50mg daily. Prior to the first dose, the subject will be counseled regarding dosing schedule, potential side effects, and the importance of adherence. A member of the study team will contact the subject by telephone at day 7 to check for tolerability.

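### Exclusion 3 in Section 5.2 names rifaximin where Section 6.4 prohibits rifampin, so a current rifampin user is not barred at entry but takes a prohibited drug from the first dose

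*Combined protocol and SAP*

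**What the plan says.** Section 5.2 gives the exclusion criteria for HIV-infected participants under the rule "Participants meeting any of the following exclusion criteria at baseline will be excluded from study participation". Exclusion 3 in that list reads "Current use of rifaximin, fluconazole or lithium given potential for drug interactions with losartan".

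Section 6.4 sets the on-study rule, introduced by "The following drugs are not permitted for HIV subjects while on study". Its list covers immunomodulators, ACE inhibitors, ARBs other than the study drug, rifampin, lithium and fluconazole.

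Section 8.1.2 fixes the timing. On eligibility it says "The designated study staff or principal investigator will sign off on lab results and eligibility criteria on the day of randomization". Of the study drug, after randomization at the same visit, it says "The drug will be dispensed to the participant to begin administration on that day".

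Section 6.3 supplies the default for other drugs: they are allowed unless the prohibited list or a package insert rules them out. It also imposes a review duty: "Whenever a concomitant medication or study agent is initiated or a dose is changed, investigators must review the concomitant medications", together with the study agents' current product information.

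**The concern.** The two lists serve one purpose, which is to keep subjects off drugs that may interact with losartan. They should therefore name the same drugs, and they differ in one name out of three. Staff who apply Section 5.2 as written have no ground in it for refusing a current rifampin user, yet Section 6.4 does not permit that person to take rifampin while on study. Because study drug starts on the day of randomization, there is no interval in which the entry rule and the on-study rule could be reconciled.

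At stake is whether a safety and eligibility rule can be followed consistently. A subject could be properly enrolled and in breach of the protocol on the same day. Conversely, a rifaximin user is turned away for a stated losartan interaction, while a subject who starts rifaximin after enrollment is not caught by the prohibited list.

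**Working it through.** There is no figure to reproduce. The check sets the two lists side by side and then looks for any other rule that would close the gap.

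**Step 1: compare the lists.** Section 6.4 follows the order of exclusions 1 to 3 in Section 5.2.

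| Item | Section 5.2 (entry) | Section 6.4 (on study) | Agree? |
|---|---|---|---|
| Immunomodulators | Exclusion 1 | Listed | Yes |
| ACE inhibitors and ARBs | Exclusion 2 | Listed (study drug excepted) | Yes |
| Fluconazole | Exclusion 3 | Listed | Yes |
| Lithium | Exclusion 3 | Listed | Yes |
| Rifaximin | Exclusion 3 | Not listed | No |
| Rifampin | Not named | Listed | No |

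Every item matches except one pair of similar names, which points to a slip in one of the lists. If both drugs were intended, each list is incomplete.

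**Step 2: look for another entry criterion that bars rifampin.**

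- The immunomodulator definition in exclusion 1 does not include rifampin among its examples.
- Inclusion 6 concerns contraindications to study procedures and names no drug.
- Exclusion 16 gives the principal investigator discretion only over suitability for surgery. The corresponding exclusion for HIV-uninfected controls (their number 6) is broader and covers suitability in general, so the HIV-infected group has no general discretionary exclusion.
- The eligibility outline in the Protocol Summary names neither drug.

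None of these excludes a rifampin user.

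**Step 3: follow the timing.** Under Section 8.1.2, eligibility is signed off, the subject is randomized and study drug is started at the baseline visit. A rifampin user who meets all the other criteria passes the sign-off, because the criteria being signed do not mention rifampin. Section 6.4 is breached at the first dose unless some other check intervenes.

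**Step 4: take the reverse direction.** A rifaximin user is excluded at entry. After enrollment rifaximin is not on the prohibited list, so under Section 6.3 it is permitted unless a package insert rules it out.

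**The case against.** The strongest reply is that the protocol, read as a whole, does not let a rifampin user take study drug. Section 6.4 forbids it outright. Section 7.1.1 collects medications at screening and baseline. Section 6.3 requires a review of concomitant drugs and product information whenever a study agent is initiated, and the first dose is such an initiation. Later, Section 7.2 adds a further check: "Levels of losartan and all ARVs that an individual subject is taking will be monitored". On this view the rule exists but sits in the wrong place, and the correction is editorial.

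Much of this stands. The checks are real and make an actual breach less likely. They do not reconcile the lists:

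- The medication history collects the fact, but the entry criterion it is compared with does not name rifampin.
- The package-insert review is a duty on the investigator and not an eligibility criterion.
- Drug-level monitoring acts after exposure. The first pharmacokinetic sampling is at Month 1 (Section 8.1.4), and the response in Section 7.2 to low losartan metabolite levels is to raise the losartan dose. Replacement under Section 9.7.2 covers only subjects withdrawn before Month 1, so someone withdrawn on the Month 1 results would not be replaced.

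It can also be said that entry criteria may properly be stricter than on-study prohibitions, so the rifaximin half is not a contradiction in itself. That is fair. It supports the reading of a name slip and should not be counted as a second defect.

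**Conclusion.** The concern holds. Sections 5.2 and 6.4 name different drugs, and rifampin is not an entry exclusion although it is prohibited on study. Confidence in the mismatch is high, since both names are plain in the text. That it is a naming slip is an inference from the otherwise matching lists, and the documents do not settle which drug was meant in Section 5.2.

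The effect is small. The documents give no frequency of use for rifampin or rifaximin, and among the 63 HIV-infected subjects planned for enrollment in Section 4.1 the number affected may be zero. They also do not say how either drug changes losartan exposure, so no pharmacokinetic or safety effect is claimed. Sample size, power, significance level and analysis are untouched. The conclusion assumes only that the hypothetical subject meets every other entry criterion and that staff apply Section 5.2 as written.

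**What to change.** Add rifampin to exclusion 3 in Section 5.2, because Section 6.4 already prohibits it. Then decide what was meant by rifaximin. If it was a slip, delete it from exclusion 3. If it was intended, add it to Section 6.4. Either way the two lists should end up naming the same drugs. The documents show no eligibility checklist, but if the site uses one it should carry the same change.

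The cost is a change of one or two drug names in a protocol amendment. Visits, sample size and analysis stay as they are.
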